1 PROTOCOL SUMMARY

1.1 SYNOPSIS

Title:	Task-dependent effects of TMS on the neural biomarkers of episodic memory
Study Description:	The Behavioral Neurology Unit studies the human brain systems underlying learning and adaptation with the goal of finding interventions to make these processes more efficient. In this study, we are interested in examining how the task state of the episodic memory network influences the effect of facilitatory TMS on memory and its EEG neural correlates. It is hypothesized that Network-targeted parietal-TMS will improve memory performance and enhance EEG biomarkers of successful memory performance, but that these changes will be modulated by the ongoing task activity during stimulation.
Objectives:	
Primary Objectives:
 
 Investigate how TMS modulates EEG neural measures of successful memory and the association of this modulation with behavioral performance Examine how memory task state influences susceptibility to plasticity via TMS and determine the optimal neural state for improving memory 
Exploratory Objectives:
 
 Search for MRI predictors of the effects of TMS
Endpoints:	
 Primary Endpoints: Memory performance, Late Positive Posterior ERP, evoked theta/alpha power (secondary), EEG functional connectivity (secondary) Exploratory Endpoints: fMRI resting state functional connectivity, fractional anisotropy
Study Population:	32 Healthy Volunteers ages 18-40. Referrals will occur from the NIH Clinical Research Volunteer program or through self-referrals to the protocol.
Description of Sites/Facilities:	Protocol activities will occur at the OP5 clinic and 7SW clinic at the NIH clinical center.
Enrolling Participants:	50 Healthy Volunteers ages 18-40

Abbreviated Title: Task-dependent TMS and memory

Version Date: 11.15.22

Study Duration: 60 months

Participant Duration: 1 month

Abbreviated Title: Task-dependent TMS and memory
Version Date: 11.15.22

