3 OBJECTIVES AND ENDPOINTS

OBJECTIVES	ENDPOINTS	JUSTIFICATION FOR ENDPOINTS
Primary		
1. Investigate how TMS modulates EEG	1. Memory performance	1. Memory performance measures will allow us to

[figure not shown]
OBJECTIVES	ENDPOINTS	JUSTIFICATION FOR ENDPOINTS

neural measures of successful memory and the association of this modulation with behavioral performance
 
2. Examine how memory task state influences susceptibility to plasticity via TMS and determine the optimal neural state for improving memory
	
 • Accuracy: Percentage of successful (later remembered hit and correct rejection) vs unsuccessful (forgotten miss and false alarm) trials for item recognition (remember/familiar/new) and context recollection (spatial location) • d': Analysis of hits (correctly remembered as encoded) relative to false alarms (new objects labelled as encoded) for item recognition 
2. Late positive posterior ERP
 
 • ERP amplitude 500-700 ms after trial onset (encoding and retrieval) over parietal and occipital electrodes 
3. Theta/alpha power (secondary)
 
 • Power in the 4-13 Hz band 0-1000 ms after trial onset (encoding and retrieval) 
4. EEG functional connectivity (secondary)
 
 • Pearson correlation coefficients (r) between electrode time courses after trial onset (encoding and retrieval) 	
examine the effects of TMS on performance, as well as to sort successful vs unsuccessful trials for EEG analyses
 
2. The late positive posterior ERP has been previously shown to be a robust marker of successful memory performance²⁵
 
3. Task-induced changes in this frequency band have been previously associated with successful memory performance²⁶
 
4. fMRI functional connectivity modulation via network-targeted TMS has been previously associated with TMS-induced memory improvement. Whether EEG functional connectivity will be similarly altered, and the relevance to memory changes, remains unknown

Tertiary/Exploratory		
1. Search for MRI predictors of the	1. Baseline fMRI functional connectivity	It is hypothesized that TMS influences downstream targets

OBJECTIVES	ENDPOINTS	JUSTIFICATION FOR ENDPOINTS

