Memory Task: This is a test of episodic memory, including item recognition and context recollection^{30,52,53}. In the task, participants will be shown a series of objects in one of four quadrants on the screen. They will be instructed to remember the objects and where they were located, both of which will be tested later. To ensure attention and for consistency with the spatial task (see below), they will be asked to indicate by button press whether the object is primarily used outdoors (e.g., a baseball) or indoors (e.g., a television). During the encoding phase, each object will be presented for 4 seconds with 4 seconds between trials. In Experiment 1, TMS will occur during a 2 second cue before each trial and in Experiment 2, TMS will occur in the first 2 seconds of stimulus object presentation. There will be 180 encoding trials, interspersed with 180 trials of the spatial task (described below). Trial order will be randomized. The retrieval phase will occur following the end of encoding. Participants will be shown, sequentially and in randomized order, the 180 encoded objects and 180 new lure objects, for a total of 360 trials. For all trials, they will respond with whether the object was old (previously seen) or new (not previously seen) and their confidence on a scale of 1-6 (1=confident new,

Abbreviated Title: Task-dependent TMS and memory

Version Date: 11.15.22

6=confident old) as a measure of item recognition. If the object was previously seen, participants will then be asked which quadrant the item was presented in to provide a measure of context recollection. We will use two different versions of the task with different and non-overlapping sets of objects at the two test sessions and the order of versions will be counterbalanced across participants.

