Stimulation will be delivered during the encoding phase of the behavioral task, either prior to trial onset (Experiment 1) or simultaneously with trial onset (Experiment 2; see 4.4.1 Behavioral Tasks for timing) in the form of 2-seconds of theta-burst stimulation (50 Hz pulse triplets every 200 ms; Figure 3) at 80% of the motor evoked potential threshold of the right abductor pollicis brevis muscle or 44% of maximum stimulator output, whichever is lower. This protocol has been

Abbreviated Title: Task-dependent TMS and memory

Version Date: 11.15.22

shown previously to particularly influence the hippocampal-cortical network and memory performance³⁷⁻³⁹.

Figure 3. Theta-burst stimulation.

EEG

Participants will be fitted with a 64-channel elastic EEG cap for the duration of each experiment session. Data will be recorded continuously during the study and test phases of the behavioral experiment. The EEG signal will be amplified online, filtered, and digitized continuously along with stimulus onset codes used for subsequent analysis. Independent component analysis and/or other processing techniques will be performed to isolate and remove recurring artifacts from the signal.

Single-trial waveforms will be screened for artifactual contamination. Trials will then be divided based on task type (spatial, memory encoding, accuracy of item recall (memory task) and spatial task performance. The timeseries from trials of the same type and/or accuracy will then be averaged, and the resulting waveforms will be compared across categories. For theta/alpha band analysis, we will additionally use time-frequency decomposition of the event-related averages.

MRI

We estimate a maximum of 1 hour for baseline scanning. Because scanner malfunctions and subsequent loss of data are common, we will not report these as unexpected problems.

Participants whose data are lost due to scanner malfunctions will be rescheduled, if possible.

Participants whose MRI sessions cannot be completed may enter the experiment if the MPRAGE (see below) data have been acquired. They will be rescheduled for the other scans when possible.

MRI anatomical scanning: All participants will have anatomical (MPRAGE) scans at baseline. Participants who have not had one in the past year will receive a standard clinical MRI scan of the head, which will be submitted to the Diagnostic Radiology Department CC for interpretation. Depending on the requirement for a clinical scan, this phase will take 10-30 min.

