8 STATISTICAL CONSIDERATIONS

8.1 STATISTICAL HYPOTHESIS

The primary aims are to investigate how TMS alters the EEG biomarkers of successful memory performance and how memory state-related neural changes influence plasticity of the brain. Secondary aims for this protocol will include examining the MRI connectivity predictors of TMS effects.

- Primary Objective 1: Investigate how TMS modulates EEG neural measures of successful memory and the relevance of modulation to behavioral performance
 - Hypotheses
 - a. Network-targeted parietal-TMS will improve memory performance (context recollection; Primary Endpoint 1) relative to vertex-TMS trials
 - b. Relative to vertex-TMS, parietal-TMS will also increase the Late Positive Posterior ERP (Primary Endpoint 2) and theta power (Primary Endpoint 3) during encoding on successful trials, relative to unsuccessful trials
 - c. Parietal-TMS will alter EEG functional connectivity patterns (Primary Endpoint 4) at encoding during successful trials relative to unsuccessful trials
 - d. The EEG effects will correlate with memory improvement (Correlation, Primary Endpoint 1 and 2-4)
 - e. Parietal-TMS will not influence neural activity or accuracy for spatial trials, relative to vertex-TMS and no-TMS
- Primary Objective 2: Examine how memory task state influences susceptibility to plasticity via TMS and determine the optimal neural state for improving memory
 - Hypotheses
 - a. Network-targeted parietal-TMS during memory encoding will have a larger effect on memory performance (Primary Endpoint 1), relative to pre-trial parietal-TMS and vertex-TMS during encoding
 - b. Exploratory Analyses:
 - i. Parietal-TMS during memory encoding will increase the Late Positive Posterior ERP (Primary Endpoint 2) and theta-power (Primary Endpoint 3), relative to pre-trial parietal-TMS and vertex-TMS during encoding
 - ii. Additionally, parietal-TMS will alter EEG functional connectivity patterns (Primary Endpoint 4) during later-remembered trials, relative to pre-trial parietal-TMS and vertex-TMS during encoding
 - iii. Network-targeted TMS will not influence neural activity during arithmetic trials, relative to vertex-TMS and no-TMS

- *Exploratory Objective:* Determine MRI predictors of the effects of noninvasive stimulation

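### Evoked theta/alpha power is taken from accuracy-sorted averages with no step to remove the noise term, so it depends on trial counts and hence on the participant's own memory score

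*Combined protocol and SAP*

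**What the plan says.** The synopsis (1.1) lists "evoked theta/alpha power (secondary" among the endpoints. Section 3 defines the measure as "Power in the 4-13 Hz band 0-1000 ms after trial onset (encoding and retrieval". Under EEG in section 4: "Trials will then be divided based on task type (spatial, memory encoding, accuracy of item recall (memory task) and spatial task performance". Then: "The timeseries from trials of the same type and/or accuracy will then be averaged, and the resulting waveforms will be compared across categories". Power is taken afterwards, from those averages: "we will additionally use time-frequency decomposition of the event-related averages".

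Three planned analyses use the result.

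- Hypothesis 1b in 8.1 compares parietal with vertex stimulation on "theta power (Primary Endpoint 3) during encoding on successful trials, relative to unsuccessful trials".
- Section 8.3.2 runs a trial type (successful, unsuccessful, spatial) by site (parietal, vertex, none) ANOVA, with emphasis on the site main effect and the interaction, at 0.025 after FDR.
- Hypothesis 1d in 8.1 (also in the objectives in section 4) correlates the EEG effects with memory improvement.

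The documents state no baseline, no matching of trial counts, no minimum count, no noise-floor correction and no single-trial power.

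**The concern.** Averaging n trials shrinks the noise but does not remove it, and squaring turns what remains into a positive offset of sigma-squared/n. Here n is the participant's number of remembered or forgotten items. Memory performance therefore enters the EEG measure mechanically, and the plan then tests that measure for a link with memory. A true success-related theta increase could be masked, a site effect could appear with no change in evoked activity, and a theta-memory correlation could arise from trial counts alone. Mean ERP amplitude does not carry this offset, because the expectation of an average does not depend on n.

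**Working it through.** **1. Trial counts (Table 1, section 4).** 2 sites x (30 + 30 + 15 + 15) = 180 per experiment, and 180 x 2 = 360 in total, as the table states. Each active site has 30 stimulated memory trials per experiment. The no-TMS condition also has 30 if Stim Off trials are pooled over both sessions (15 + 15).

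**2. Expectation.** With evoked power m and single-trial noise power s2, E(power of an n-trial average) = m + s2/n. At 80% accuracy, 30 x 0.20 = 6 trials remain in the unsuccessful cell.

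**3. Bias with no baseline.** T trials per site, parietal accuracy p, vertex accuracy v, in units of s2:

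- Contrast: [1/(Tp) - 1/(T(1-p))] - [1/(Tv) - 1/(T(1-v))]
- Site main effect: {[1/(Tp) + 1/(T(1-p))] - [1/(Tv) + 1/(T(1-v))]}/3, with the spatial cells cancelling at equal counts.

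For T = 30, v = 0.70, p = 0.80:

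- Contrast: (1/24 - 1/6) - (1/21 - 1/9) = -0.1250 + 0.0635 = -0.0615.
- Site: [(1/24 + 1/6) - (1/21 + 1/9)]/3 = (0.2083 - 0.1587)/3 = +0.0165.

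| Vertex to parietal accuracy | Contrast | Site |
|---|---|---|
| 70 to 75% | -0.025 | +0.006 |
| 70 to 80% | -0.062 | +0.017 |
| 80 to 90% | -0.171 | +0.054 |
| 80 to 70% | +0.062 | -0.017 |
| 45 to 55% | -0.027 | 0.000 |
| 40 to 50% | -0.028 | -0.002 |

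The sign thus depends on the direction of the accuracy change and, for the site effect, on whether accuracy moves away from 50%. Pooling both experiments (T = 60) halves every entry.

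**4. False rejection.** Simulated studies of N = 32, T = 30, the same expected evoked signal in every cell, binomial counts, power over 10 independent bins, accuracy SD 0.10, true-gain SD 0.05. Tests at 0.025 before FDR: one-sample t for the contrast, three-level repeated-measures F for site. The ratio is m/s2. Rise from 70 to 80%:

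| Ratio | 0.1 | 0.3 | 1 | 3 |
|---|---|---|---|---|
| Contrast, no extra variation | 60% | 38% | 16% | 7% |
| Contrast, lognormal SD 0.3 in cell and session power | 53% | 25% | 6% | 3% |
| Site, no extra variation | 49% | 29% | 11% | 5% |
| Site, with that variation | 26% | 9% | 3% | 3% |

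A separate run with the same assumed SD gave 44, 19 and 5% (contrast) and 25, 9 and 4% (site) at ratios 0.1, 0.3 and 1. For 70 to 75% it gave 12, 6 and 2% and 7, 4 and 4%. With no accuracy shift both tests reject 2-3%.

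**5. Correlation.** Let k be the number of successes at a site. The term 1/k - 1/(T-k) falls as k rises, while 1/k + 1/(T-k) rises with k once k exceeds T/2. Chance variation in k also enters item gain. So the success contrast correlates negatively with gain, and the overall site difference correlates positively when accuracy is above 50%. With no mean TMS effect, accuracy 60-70%, ratios 0 to 1 and no extra variation, the success contrast gives:

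- item gain: mean r -0.21 to -0.66, rejecting 14-99%;
- context correct over all encoded objects: -0.13 to -0.41, 7-57%;
- context scored over hits only: about 2%.

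The site difference correlates at about +0.2 to +0.4 with item gain at ratios 0.1 to 1. Extra variation would dilute these correlations.

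**6. If a baseline were used.** Same-average baseline power has expectation s2/n, so subtracting it leaves m (rejections 2-4%). Dividing by it leaves about 1 + n x m/s2, which grows with n. A dB baseline therefore reverses the contrast bias to upward, with rejections of 23, 50, 70 and 76% at ratios 0.1, 0.3, 1 and 3 (70 to 80%, no extra variation).

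**7. Corrected estimator.** Mean single-trial power has expectation m + s2. Hence E(n x power of average - mean single-trial power) = nm + s2 - m - s2 = (n-1)m, and dividing by n-1 gives m for any n. In simulation all three analyses then reject 1-4%.

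**The case against.** The strongest reply is that neither the trigger nor the sign is fixed by the documents.

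- **Baseline.** The plan is silent. Section 3 justifies the endpoint by task-induced change, which fits a baseline-referenced measure too. This stands: the signs in steps 3 to 5 hold only with no baseline. It does not rescue the plan, since the unstated choice decides whether the bias is absent, downward or upward.
- **Trigger.** Hypothesis 1a predicts better context recollection, whereas sorting is on item accuracy. This stands for the ANOVA, although section 3 includes item recognition in the memory endpoint. The correlation problem needs no mean TMS effect, but it largely vanishes if context is scored over hits only.
- **Equal counts.** Artefact screening, or splitting spatial trials by performance, could make other cells unequal, and pooling of Stim Off trials is not stated. This stands as an assumption; differing counts would be a further source of the same bias.
- **Size.** Realistic variation brings the ANOVA tests near nominal by ratio 1. For a 5-point gain this happens from about 0.3 for site and about 1 for the contrast. High ratios are plausible in Experiment 2: "in Experiment 2, TMS will occur in the first 2 seconds of stimulus object presentation", with "50 Hz pulse triplets every 200 ms", that is 5 Hz, inside the band and the window. In Experiment 1 stimulation precedes the trial.

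A reader might infer that any TMS effect on accuracy will hide the success effect and create a false parietal theta effect. The documents do not support that: a fall from above 50% reverses both signs, 45 to 55% gives no site bias, and the accuracy level and signal ratio are not given.

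**Conclusion.** The stated method yields a power measure that depends on trial count, and no stated step corrects it. With no baseline and a rise in item accuracy from 70 to 80% on 30 trials, the biases are -0.062 (contrast) and +0.017 (site) sigma-squared. They matter at evoked/noise ratios of about 0.3 or less and are small at 3. The theta-memory correlation can be spurious without any mean TMS effect: negative for the success contrast, positive for the overall site difference above 50% accuracy. Accuracy, ratio, number of bins and variances are assumptions, and the rates are before FDR.

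It would go too far to conclude that the trial's main result is compromised. The sample size in 8.2 rests on memory performance and the late positive ERP. Theta/alpha is secondary in 1.1, section 3 and the objectives in section 4, although 8.1 numbers it Primary Endpoint 3. This should be corrected before analysis.

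**What to change.** Add to the EEG part of section 4 and to 8.3.2:

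*Evoked theta/alpha power in each participant, site and trial-type cell is (n x power of the n-trial average - mean single-trial power)/(n-1), with n the retained trials; this value is used for the site main effect, the trial type by site interaction and contrast, and the correlation with memory improvement.*

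An alternative is repeated random subsampling to equal counts across the compared cells. A dB or ratio baseline on each cell average should not be relied on.

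The cost is single-trial decomposition, which is code only and needs no new data. Corrected values can be negative (about 54% of cells at ratio 0, at most 0.3% at ratio 0.3 or more), so they cannot be log-transformed. Cells with fewer than 2 trials are lost. Under the assumed accuracies this removes 0.5-13% of participants from a complete-case ANOVA of this endpoint at 30 trials, and 0.1-5% at 60. No loss of precision was seen in simulation: the SD of the contrast was 0.65 to 1.00 times that of the uncorrected measure.

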4.1 CONCOMITANT THERAPY

Not applicable

5 STUDY POPULATION

5.1 INCLUSION CRITERIA

In order to be eligible to participate in this study, an individual must meet all of the following criteria:

1. Stated willingness to comply with all study procedures and availability for the duration of the study
2. Ability of subject to understand and the willingness to sign a written informed consent document.
3. Age 18-40 (inclusive)

5.2 EXCLUSION CRITERIA

An individual who meets any of the following criteria will be excluded from participation in this study:

- 1.) Any current major neurological or psychiatric disorder such as (but not limited to) stroke, Parkinson disease, Alzheimer disease, schizophrenia or major depression
- 2.) History of seizure
- 3.) Medications acting on the central nervous system, such as those that lowers the seizure threshold such as neuroleptics, beta lactams, isoniazid, metronidazole; benzodiazepines, tricyclic or other antidepressants; or prescription stimulants.
- 4.) Inability to provide informed consent
- 5.) Ferromagnetic metal in the cranial cavity or eye, implanted neural stimulator, cochlear implant, or ocular foreign body
- 6.) Implanted cardiac pacemaker or auto-defibrillator or pump
- 7.) Non-removable body piercing
- 8.) Claustrophobia
- 9.) Inability to lie supine for 1 hour
- 10.) Pregnancy, or plans to become pregnant during the study.
- 11.) Members of the NINDS BNU
- 12.) Subjects who have contraindications to MRI will follow the NMR Center guidelines for MR safety

An eligibility checklist is provided in Appendix A.

5.3 INCLUSION OF VULNERABLE PARTICIPANTS

5.3.1 Participation of Employees

NIH employees may be enrolled in this study as this population meets the study entry criteria. Neither participation nor refusal to participate as a subject in the research will have an effect, either beneficial or adverse, on the participant's employment or position at NIH.

Every effort will be made to protect participant information, but such information may be available in medical records and may be available to authorized users outside of the study team in both an identifiable and unidentifiable manner.

The NIH Information Sheet on Employee Research Participation will be made available. Please see section **9.1.5** for consent of employees.

5.3.2 Women who are Pregnant, Plan to Become Pregnant, or are Breast-feeding

The effects of MRI on fetal development and the health of pregnant women is unknown. Therefore, women of childbearing potential will have a pregnancy test before each MRI session. Women who are pregnant will be excluded and women who can become pregnant will be excluded following a positive pregnancy test.

5.3.3 Adults who lack capacity to consent

Adults who are unable to provide initial informed consent will be excluded from this study. Adults who permanently lose the capacity to provide on-going consent subsequent to giving initial consent will be removed from the study and compensated for what they have completed.

5.4 LIFESTYLE CONSIDERATIONS

Not applicable

5.5 SCREEN FAILURES

Screen failures are defined as participants who consent to participate in the clinical study but are not subsequently entered in the study. A minimal set of screen failure information is required to ensure transparent reporting of screen failure participants, to meet the Consolidated Standards of Reporting Trials (CONSORT) publishing requirements and to respond to queries from regulatory authorities. Minimal information includes demography, screen failure details, eligibility criteria, and any serious adverse event (SAE).

Individuals who do not meet the criteria for participation in this study (screen failure) because of a medication or pregnancy may be rescreened. Rescreened participants should be assigned the same participant number as for the initial screening.

